1.2 Risk/benefit assessment

The application of LISA technique allows administration of surfactant without interrupting the non-invasive respiratory support, so avoiding the need for intubation and administration of

invasive positive pressure ventilation even for a short period.

The LISA technique, as well as other methods for less invasive surfactant administration through thin catheter, have been evaluated in several IIT and compared with conventional surfactant administration through endotracheal tube (including application of an intubation, surfactant administration and rapid extubation procedure). Even with limitations related to the heterogeneity and quality of the studies, recent meta-analysis showed that benefits associated with less invasive surfactant methods include reduced need for MV and reduced rate of mortality and BPD [17,18]. Moreover, some recent studies have also suggested a reduction in the incidence of Retinopathy of prematurity (ROP) and Intraventricular hemorrhage (IVH) in neonates receiving surfactant through LISA technique [19,20].

Some transient adverse events, including oxygen desaturation, apnea, bradycardia, coughing, choking, sneezing, and surfactant reflux, have been observed more frequently during LISA procedure compared to conventional administration [17,21,22]. These events are usually mild and easily managed. In a recent large cohort study, an increased risk of focal intestinal perforation (FIP) (10% vs 7.4%) was observed in the subgroups of neonates <26 weeks GA [19]. The authors suggest that other factors, beside LISA, could contribute to the pathogenesis of FIP in this population of highly vulnerable neonates, including: early exposure to maximum CPAP levels, modulators of mucosal integrity (devices, bacterial colonization, nutrition, drugs), delayed meconium passage, and frequency of episodes of relevant desaturation (leading to temporary hypoxia of the gut).

Considering the above reported information, the safety profile of the treatment, the measures in place to ensure the patients' safety and the expected scientific value, the overall risk/benefit assessment can be considered acceptable for the proposed trial.

2. STUDY OBJECTIVES

2.1 Primary Objective(s)

The main objective of this study is to evaluate the safety profile of the administration of porcine surfactant (poractant alfa, Curosurf®) through a less invasive method (LISA) using a thin catheter (CHF 6440) during non-invasive ventilation (NIV) (CPAP, NIPPV, BiPAP), compared to an approved conventional surfactant administration during invasive ventilation and rapid extubation, in spontaneously breathing preterm neonates with clinical signs of respiratory distress syndrome (RDS). The short-term and mid-term safety will be assessed: adverse events and adverse drug reactions occurring during overall procedure for surfactant administration, neonatal pain assessment pre- and during surfactant administration, duration of surfactant administration, incidence of BPD at 36 weeks post menstrual age (PMA), major neonatal morbidities and vital signs.

2.2 Secondary Objective(s)

Moreover, short-term and mid-term efficacy profile will also be assessed mainly in terms of: reduced oxygen requirement and ventilatory support, need for invasive mechanical ventilation in the first 72 hours of life and throughout the study period, duration of invasive and non-

invasive ventilation and need for additional surfactant doses.

3. STUDY DESIGN

This is an open-label, multicenter, randomized and controlled study. Approximately 25 investigational sites will be involved in US. Neonates will be evaluated according to the selection criteria and then randomized to surfactant treatment via LISA or standard administration procedure ([Table 1](#)). The enrollment will be staggered: the gestational age will be restricted to 27⁺⁰ weeks up to 28⁺⁶ completed weeks until safety evaluation by ISMB is performed for the first 15 neonates. Provided no safety concerns are raised, the enrollment will then be extended to the whole population (i.e. 25⁺⁰ weeks up to 28⁺⁶ completed weeks).

[figure not shown]
Enrolled neonates will be evaluated:

- until discharge,
- until 40 weeks PMA (if still in hospital),
- if discharge occurs before 36 weeks, the last evaluation will be at 36 weeks PMA.

This period represents the main phase of the trial.

Their final assessment of development will be at 24-month corrected age as a separate stand-alone visit. This 24-month clinical assessment will be analyzed and evaluated separately from the initial part of the study and will be object of an addendum to the initial core clinical study report.

Table 1: TIMETABLE

End of the trial

The end of the trial will correspond to the last evaluation of the last neonate from the recruiting site or from the continuing care site in case the treated baby was transferred from the original recruiting site. The last evaluation could be:

- the date of the assessment for BPD diagnosis (i.e. 36 weeks PMA) if the patient is discharged home before 36 weeks PMA,
- discharge home (if discharged between 36 weeks and 40 weeks PMA), or
- 40 weeks PMA (if still in hospital).

4. SUBJECT SELECTION CRITERIA

4.1 Subject Recruitment

The study population consists of premature neonates with early clinical signs of RDS, spontaneously breathing and stabilized with NIV (CPAP, NIPPV, BiPAP). One hundred and fifty (150) subjects who meet all the inclusion and none of the exclusion criteria are expected to be randomized in the study. No limitation by ethnic origin or social status will be used. RDS is defined in this study population by the presence of respiratory symptoms and signs, associated to an increased inspired oxygen requirement, from 30 minutes up to the first 24 hours of life.

4.2 Inclusion Criteria

Subjects must meet all the following inclusion criteria to be eligible for enrolment into the study:

1. Written informed consent obtained by parents/legal representative (according to local regulation) prior to or after birth;
2. Preterm neonates of either sex aged ≥ 30 minutes and < 24 hours, spontaneously breathing and stabilized on NIV;
3. Gestational age of 25^{+0} weeks up to 28^{+6} completed weeks; enrollment will be restricted to subjects aged 27^{+0} weeks up to 28^{+6} GA weeks until safety evaluation of first 15 subjects is completed;
4. Clinical course consistent with RDS;
5. Fraction of inspired Oxygen (FiO_2) ≥ 0.30 to maintain preductal SpO_2 in the target range of 88–95%.

4.3 Exclusion Criteria

The presence of any of the following criteria will exclude a subject from study enrollment:

1. Need for immediate endotracheal intubation for cardiopulmonary resuscitation or insufficient respiratory drive;

2. Use of nasal high frequency oscillatory ventilation (nHFOV) prior to study entry;
3. Use of surfactant prior to study entry and need for intratracheal administration of any other treatment (e.g. nitric oxide);
4. Known genetic or chromosomal disorders, major congenital anomalies (congenital heart diseases, myelomeningocele, etc.);
5. Mothers with prolonged premature rupture of the membranes (> 21 days duration) which could cause complications (in particular, severe pulmonary hypoplasia due to oligohydramnios);
6. Presence of air leaks if identified and known prior to study entry;
7. Evidence of severe birth asphyxia (e.g. continued need for resuscitation at 10 minutes after birth, altered neurological state or neonatal encephalopathy);
8. Neonatal seizures prior to study entry;
9. Any condition that, in the opinion of the Investigator, would place the neonate at undue risk;
10. Participation in another clinical trial of any medicinal product, placebo, experimental medical device or biological substance conducted under the provisions of a protocol on the same therapeutic target; the participation in studies involving diagnostic devices or studies with treatments for different conditions than lung and respiratory function impairments may be permitted following an agreement with the sponsor. Non-interventional observational studies are allowed.

4.4 Subject Withdrawals

Parents/legal representative have the right to withdraw the subject from the study at any time for any reason.

The Investigator also has the right to withdraw the subjects from the study in the event of:

- An adverse event which is considered intolerable by the Investigator prior to surfactant administration.
- An abnormal laboratory test result that the Investigator considers clinically significant and warranting the withdrawal of the subject prior to surfactant administration.
- A concomitant clinical condition/disorder/anomaly that necessitates pharmacological treatment with a drug which interacts in any way with the study treatment prior to surfactant administration.
- Hypersensitivity to the active substance or to any of the excipients with regards to the second and third possible treatments with proactant alfa (if needed).
- The development of any exclusion criterion prior to surfactant administration.

Detection of COVID-19 infection at the enrollment or during the study does not automatically lead to withdrawal of the subject. It will be up to the investigator's judgement to withdraw

the subject from the study if he/she deems that remaining in the study will place the subject and/or the clinical site at undue risk by continuing their participation. The investigator/site staff must take all necessary precautions to minimize and avoid the risk of transmission and exposure to study subjects and site staff, according to local guidelines.

The Investigator is responsible for the optimal individual treatment for the subject. The Investigator must complete the “Study Termination” page of the electronic case report form (eCRF) explaining the main reason for withdrawal.

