Following direct laryngoscopy, the catheter will be introduced orally and inserted through the vocal cords into the trachea to the desired depth of 1-2 cm, the laryngoscope will be carefully removed while the catheter is secured by the fingers of the neonatologist/investigator, who will finally close the neonate's mouth. The correct position of the catheter into the trachea will be confirmed by the visualization of tip depth markings and by the tip-to-lip measurement. The thin catheter presents three different ring markings close to the tip, equal to 1, 2 and 3 cm ([Figure 1C](#)) and helpful to address the depth of insertion beyond the vocal cords. Moreover, the catheter presents markings going from 5 to 9 cm for the tip-to-lip measurement, which represents the standard method to estimate the correct position also of the ETT [\[23\]](#).

After having confirmed the correct position of the catheter into the trachea, the syringe filled with poractant alfa suspension will be connected to the Luer of the catheter and poractant alfa will be instilled over 0.5-3 minutes with careful observation of the neonate's continuous spontaneous breathing. Once the surfactant is administered, the catheter will be removed. Before removing the LISA catheter, it should be fully cleared of surfactant with some additional air. After completion of surfactant administration, ventilatory support may require transient adjustments. Airways suction should not be performed for 1 hour after surfactant instillation, unless signs of significant airway obstruction occur.

If on the first attempt the catheterization of the trachea is not possible within 30 seconds, the laryngoscope should be removed and if required neonate's recovery allowed. Then a second

attempt should be performed for a total number of 3 attempts.

Details of the procedure as well as neonate's vital signs and any occurring adverse event will be recorded according to the time points of the protocol by the team member assisting or observing the procedure.

Figure 1: CHF 6440

Figure 1A
CHF 6440 Full View

Figure 1B
Close-up on CHF 6440 Components

a) Standard Luer

b) Rounded and Soft Tip

[figure not shown]

Figure 1C
Close-up of Markings Present on CHF 6440 Shaft

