7.1.2 Day 1 - From study treatment administration to 24 hours post-treatment

Once the neonate's eligibility to take part in the study is confirmed, the Investigator will have to call/check the IRT to randomize the neonate to the treatment group (LISA or ETT).

Before starting the procedure:

Within 15 minutes before starting the procedure (before laryngoscope insertion), the following information will be collected:

- SpO_2 along with vital signs (systolic, diastolic and mean blood pressure, heart rate, respiratory rate);
- Fraction of inspired oxygen (FiO_2);
- Type of respiratory support (CPAP, BiPAP, NIPPV);
- Non-invasive ventilation parameters (CPAP pressure, BiPAP pressures, NIPPV peak pressure, PEEP, mean airway pressure);
- Pain score assessment (PIPP score) [26] by observing the subject for 15 seconds (see [APPENDIX IV](#));
- Blood gas analysis (values of pH, pCO_2 , pO_2 , HCO_3 , BE, lactate), unless the time from the blood gas analysis at screening is less than 1 hour. In this case only one blood gas analysis is acceptable;
- All medical conditions diagnosed before treatment drug administration, to be reported as "Medical History", including congenital conditions that could be diagnosed after study treatment administration;
- Concomitant Medications.

After Starting the Procedure:

From the start of the procedure (laryngoscope insertion) through the first 24 hours from administration, the following information will be collected:

- SpO_2 and FiO_2 at time 0 (end of surfactant administration), and at 5, 15, 30 min, 1 hour, 6, 12 and 24 hours after the end of study treatment administration;
- Vital signs (SDB, DBP, MBP, HR, RR): 15, 30 min, 1 hour, 6, 12 and 24 hours after the end of study treatment administration; HR and RR to be reported also at time 0 and 5 min (as showed in flow chart [Table 2](#));
- Evaluation of respiratory support: any change in non-invasive ventilation, need for intubation and invasive mechanical ventilation with the relevant dates and times;
- If applicable, NIV parameters (as specified above) at 30 minutes, 1 hour, 6, 12 and 24

- hours after the end of treatment administration;
- Evaluation of oxygen alone use: duration of needing supplementary oxygen with the relevant dates and times;
- PIPP score immediately following surfactant administration after observing the neonates for 30 seconds (see [APPENDIX IV](#));

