8. EFFICACY ASSESSMENTS

The following variables will be used to describe the efficacy of the two procedures:

- Percentage of neonates needing invasive mechanical ventilation (MV) in the first 72 hours of life, 28 days PNA and within 36 weeks PMA defined as follows:

ETT group

- neonates not extubated within 1 hour from initial surfactant administration and receiving MV for more than 1 hour;
- neonates extubated and re-intubated to receive MV of any duration.

LISA group

- neonates intubated to receive MV of any duration,
 - Duration of invasive ventilation (hours) in the first 72 hours of life, 28 days PNA and within 36 weeks PMA;
 - Percentage of neonates needing any intubation procedure, outside the initial surfactant administration period, in the first 72 hours of life, in the first 28 days PNA and within 36 weeks PMA;
 - SpO₂ at time 0 (study treatment administration), 5, 15, 30 minutes, at 1, 6, 12, 24, 48, 72 and 120 hours post treatment; additionally, at 28 days PNA and at 36 weeks PMA for neonates still receiving any form of respiratory support;
 - FiO₂ at time 0 (study treatment administration), 5, 15, 30 minutes, at 1, 6, 12, 24, 48, 72 and 120 hours post treatment; additionally, at 28 days PNA and at 36 weeks PMA for neonates still receiving any form of respiratory

support;

- SpO₂/FiO₂ at time 0 (study treatment administration), 5, 15, 30 minutes, at 1, 6, 12, 24, 48, 72 and 120 hours post treatment; additionally, at 28 days PNA and at 36 weeks PMA for neonates still receiving any form of respiratory support;
- Percentage of neonates needing additional surfactant doses and number of surfactant doses;
- Duration of oxygen alone supplementation (days) and any non-invasive ventilation during the study (days);
- Blood gas analysis, specifically acid-base balance parameters (i.e. pH, pCO₂, pO₂, HCO₃, BE, lactate) pre-surfactant administration (when applicable), at 1 hour, 6 hours, 24, 48 and 72 hours after study treatment.

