12.2. Populations for analysis

The following populations will be considered for the analysis:

- **Intention-to-Treat population (ITT):** all randomized subjects who will receive at least one dose of study medication.
- **Safety population:** all randomized subjects who will take at least one dose of study medication.

The efficacy analyses population will be performed in the ITT population. The Safety population will be used in the analysis of all safety variables.

In case of deviation between as-randomized treatment and treatment actually received, the treatment actually received will be used in the safety analyses (i.e. an as-treated analysis will be performed).

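### Open-label withdrawal for exclusion criteria arising before surfactant, combined with dosed-only analysis sets, can remove undosed neonates from efficacy and safety analyses, probably in favour of LISA on need for MV

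*Protocol*

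**What the plan says.** - **Order of events.** Section 3: "This is an open-label, multicenter, randomized and controlled study". Under section 7.1.2, once eligibility is confirmed "the Investigator will have to call/check the IRT to randomize the neonate to the treatment group (LISA or ETT"). Pre-procedure assessments, laryngoscopy and instillation come afterwards. In the LISA arm, section 6.2.3.3 allows repeated catheterisation: a second "attempt should be performed for a total number of 3 attempts". Every neonate therefore passes through a period of being randomised but undosed.
- **Withdrawal.** Section 4.4: "The Investigator also has the right to withdraw the subjects from the study in the event of" several listed situations, one of which is "The development of any exclusion criterion prior to surfactant administration". The exit is recorded on a study termination page. The section does not distinguish stopping the treatment from ending data collection.
- **The criteria that can be re-applied.** Section 4.3, criterion 1: "Need for immediate endotracheal intubation for cardiopulmonary resuscitation or insufficient respiratory drive". Criterion 9 is any condition that in the investigator's opinion puts the neonate at undue risk.
- **Need for MV.** Section 8 counts, in the LISA group, "neonates intubated to receive MV of any duration". In the ETT group it counts MV for more than one hour without extubation, or re-intubation for MV.
- **Analysis sets.** Section 12.2 defines ITT as "all randomized subjects who will receive at least one dose of study medication" and uses it for efficacy. The Safety population carries the same dose requirement and is used for all safety variables.

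**The concern.** An entry criterion that can be applied again after a known allocation acts as a post-randomisation filter. The same deterioration before instillation has a different standing in the two arms. In the ETT arm, intubation is what the neonate was assigned to receive. In the LISA arm, it departs from the strategy and, if done for MV, is an efficacy event. If the LISA neonate is withdrawn before any dose, that event goes uncounted and the denominator shrinks with it.

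The safety objective, which is the main one (section 2.1), is exposed as well. Section 10.8 starts the procedure at laryngoscope application. Section 9 lists failed first attempts, discontinued manoeuvres and adverse events during the procedure. A neonate whose insertion is abandoned before instillation and who is then withdrawn is not in the set used to analyse those variables. Follow-up for mortality and BPD at 36 weeks PMA may also end, in neonates likely to be among the sickest.

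**Working it through.** **Is the route open in the text?**

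1. Randomisation precedes the procedure and is open label (sections 3, 7.1.2).
2. From then until surfactant is given, the section 4.4 ground applies. Its only time limit is surfactant administration.
3. A neonate who loses respiratory drive or needs immediate intubation in that interval meets criterion 1 and may be withdrawn. Criterion 9 adds a ground resting on judgement.
4. If no study poractant alfa is given, section 12.2 places the neonate outside both ITT and Safety. No other section of the protocol brings the neonate back into an analysis, and section 7.2.3 plans BPD assessment for treated subjects.

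The loss needs both steps: section 4.4 allows the exit, and section 12.2 turns it into exclusion from analysis.

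**How large could it be?** The plan offers no figure to reproduce. Section 12.1 gives 100 + 50 = 150 neonates at 2:1, with no power calculation and no expected MV rate. The event rates and numbers lost below are therefore assumptions.

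Let p be the true LISA rate and k the number of LISA events withdrawn undosed, with no control losses. The observed LISA rate is (100p − k)/(100 − k).

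- p = 30%, k = 2: 28/98 = 28.6%, a shift of 1.4 points.
- p = 30%, k = 5: 25/95 = 26.3%, a shift of 3.7 points.

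Over a wider range, with the same true rate p in both arms and 50 controls intact:

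| p | k = 3 | k = 5 | k = 10 | 95% CI half-width, no losses |
|---|---|---|---|---|
| 20% | 17/97 = 17.5% | 15/95 = 15.8% | 10/90 = 11.1% | 13.6 points |
| 40% | 37/97 = 38.1% | 35/95 = 36.8% | 30/90 = 33.3% | 16.6 points |
| 60% | 57/97 = 58.8% | 55/95 = 57.9% | 50/90 = 55.6% | 16.6 points |

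The half-width is 1.96 × √[p(1 − p)(1/50 + 1/100)]. The shift runs from 1.2 points (p = 60%, k = 3) to 8.9 points (p = 20%, k = 10). A single loss moves the rate by less than 1 point.

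The effect on a nominal two-sided 5% comparison was approximated with an unstratified two-proportion normal test (pooled variance for the critical value). For p = 20% and k = 5 the difference is 20.0 − 15.8 = 4.2 points and the rejection probability is 10.5%. For p = 40% and k = 5 it is 6.7%.

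**What if controls are lost too?** Take a true rate of 30% in both arms, so 15/50 in control. Losing 2 LISA events and 1 control event gives 28/98 = 28.6% and 14/49 = 28.6%, a net bias of zero. The bias therefore depends on uneven losses, not on losses as such.

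**The case against.** The case on the other side has several parts, and much of it stands.

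- **Section 4.4 removes nobody from an analysis by itself.** Correct. With an all-randomised ITT, most of the problem would go. What would remain is missing follow-up after withdrawal.
- **A reader might infer that criterion 1 is the efficacy event itself.** The text does not support that. Criterion 1 concerns immediate intubation for resuscitation or insufficient drive. The section 8 event is intubation to receive MV, and section 6.2.3.7 has its own criteria for MV. They overlap without being identical.
- **A reader might infer that the control arm is untouched.** The documents do not show this. The rule is worded identically for both arms, and a control neonate who deteriorates before instillation may also be withdrawn undosed. Uneven loss is likely because of what intubation means in each arm, but no zero loss in control can be claimed.
- **A reader might infer that every failed LISA placement is lost.** Not so. Withdrawal is a right, not a duty. A LISA neonate who is intubated and then given poractant alfa through the tube is dosed and stays in. Failing the permitted attempts is not an exclusion criterion, and section 6.2.3.5 on resuscitation does not mention withdrawal.
- **The separate any-intubation variable is not clearly affected.** Section 8 confines it to intubation outside the initial surfactant administration period, so intubation during placement arguably falls outside it even if the neonate is retained.
- **Need for MV is a secondary-objective variable in a descriptive study** with no primary efficacy endpoint, and the interval half-widths exceed the shifts calculated here. This limits the weight of the point. It does not remove a distortion with a likely direction.

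The matter cannot be left wholly to an SAP, which was not available here. Section 12.2 already fixes both populations, and an analysis plan cannot recover 36-week outcomes that were never collected.

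**Conclusion.** The point holds in a limited form. Together, sections 4.4 and 12.2 allow a neonate randomised with known allocation to be withdrawn undosed for a newly arising exclusion criterion and so to leave both the efficacy and the safety analyses. The likely direction on need for MV favours LISA. The dosed-only Safety set can also drop failed or discontinued insertions and procedural adverse events, which belong to the main objective.

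The size is unknown. The shift of 1.4 to 3.7 points is an illustration that assumes a 30% true LISA rate, 2 to 5 lost neonates who were all events, and no control losses. It is not an estimate of net bias. The effect is modest unless several neonates are lost, but the remedy is cheap and worth making.

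**What to change.** 1. **Section 12.2, efficacy.** Define ITT as all randomised neonates, analysed as randomised. State that a LISA neonate intubated for MV between randomisation and instillation counts as a need-for-MV event. Leave the separate variable for intubation outside the initial administration period as defined.
2. **Section 12.2, safety.** Include every neonate in whom the procedure was started, that is, from laryngoscope insertion, whether or not a dose followed.
3. **Section 4.4.** Separate not receiving or stopping study treatment from withdrawal from follow-up. Do not use exclusion criteria that arise after randomisation as grounds for ending data collection. Continue to collect respiratory support, mortality and BPD from routine records unless the parents withdraw consent.

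These changes concern data collection and analysis only. Bedside management and the decision to stop a procedure remain with the protocol and the investigator. The cost is wording in two sections and record-based follow-up of what should be a few neonates.
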